9.4 Randomization

Randomization is not applicable, as this is a single arm study design.

9.5 Analysis Populations

The following analysis populations are defined for utilization in the data analysis:

- **Intent to treat patient population (ITT):** The ITT subject population will include all enrolled subjects who have met all inclusion/exclusion criteria.
- **Safety Population:** The safety population will include all enrolled subjects that undergo induction of anesthesia.
- **Per protocol patient population (PP):** The PP patient population will include all subjects who complete both the Epicardial Surgical Ablation Procedure and Endocardial EP Ablation Procedure.

- **AtriClip Effectiveness population:** The AtriClip effectiveness population will include all ITT subjects for whom an attempt (entrance of the AtriClip into the chest wall) is made to place an AtriClip device.

The primary effectiveness analysis will utilize the ITT patient population. Secondary effectiveness analyses will be conducted on the ITT and the PP patient populations. All safety analyses will utilize the safety population.

9.6 Secondary Endpoints

9.6.1 Secondary Endpoints – Effectiveness

For labeling purposes, to be tested if the primary effectiveness endpoint is a success:

1. Exclusion of the LAA, defined as defined by lack of fluid communication (<3 mm residual communication with LAA and < 10mm residual pocket) between the LA and LAA. This endpoint will be measured at the 12-Month (Visit 11) (approximately 15 months post AtriClip placement). The AtriClip effectiveness population will be utilized for analysis of this endpoint.

Based on a literature review of peer-reviewed research that was performed for the EXCLUDE trial (add reference here for the trial), a weighted average rate of 77.5% exclusion at 3 months was derived as a reasonable expectation of success, based on a combination of cut and sew and stapling procedures³⁵⁻⁴⁴. That same trial resulted in actual exclusion rates of 95.7% (67/70) for intra-procedural success and 98.4% (60/61) for 3-month success. Utilizing the most conservative of these results gives a 95% lower confidence limit of just under 88% for an exact binomial confidence interval.

In the current study, it is believed that the placement of a clip will provide a significant benefit to the patient with extremely low added safety risk. A success rate of over 80% will exceed the 77.5% expectation of success based on other exclusion methods, with less risk of injury than those methods³⁵⁻⁴⁴, and is a reasonable expectation based on the EXCLUDE results that showed a lower bound of just under 88%. The associated hypothesis test, based on an exact binomial confidence interval, will be as follows:

$$H_o : p_2 \leq .80 \quad vs. \quad H_a : p_2 > .80$$

Exploratory endpoints:

2. Exclusion of the LAA, defined as lack of fluid communication (<3 mm residual communication with LAA and <10 mm residual pocket) between the LA and LAA. The endpoint will be measured intra-procedurally (Visit 2), and at the Endocardial EP Ablation Procedure (Visit 5). The AtriClip effectiveness population will be utilized for analysis of this endpoint.
3. Acute procedural success of surgical epicardial procedure, defined as the percentage of subjects with successful electrical isolation/block of all pulmonary veins, as well as the “box”. The ITT and PP populations will be utilized for analysis of this endpoint.
4. Acute procedural success of endocardial catheter procedure, defined as the percentage of subjects with successful electrical isolation/block of all pulmonary veins and the “box”, as well as bi-directional block of the cavo-tricuspid isthmus. The ITT and PP populations will be utilized for analysis of this endpoint.
5. Freedom from Atrial Fibrillation, Atrial Tachycardia, Atrial Flutter without AAD, defined as no documented event >30 seconds in duration (or for the entire length of an ECG tracing) with no utilization of AADs beyond the blanking and AAD optimization period, except as previously failed without an increase in dose. This endpoint will be measured through the 12-month, 2-, 3-, 4-, and 5-year visits (Visits 11-15) via cumulative ECG monitoring. The ITT and PP populations will be utilized for analysis of this endpoint.

6. Freedom from Atrial Fibrillation, Atrial Tachycardia, Atrial Flutter regardless of AAD, defined as no documented event >30 seconds in duration (or for the entire length of the ECG tracing) regardless of AAD usage. This endpoint will be measured through the 12 month, 2-, 3-, 4-, and 5-year visits (Visits 11-15) via cumulative ECG monitoring. The ITT and PP populations will be utilized for analysis of this endpoint.
7. Freedom from any documented AF, atrial flutter, or atrial tachycardia lasting >10 minutes duration through the 12-month follow-up visit in the absence of Class I or III AADs (with the exception of previously failed AADs at doses not exceeding those previously failed). The ITT and PP populations will be utilized for analysis of this endpoint.
8. Change in Quality of Life, defined as the total AFEQT score measured at the 12-month follow-up visit minus the score at the baseline visit. The score will be calculated per the AFEQT scoring manual. The ITT and PP populations will be utilized for analysis of this endpoint.

9.6.2 Secondary Endpoints – Safety

All secondary safety endpoints are supplemental and intended to provide a more complete picture of the overall safety profile for the DEEP procedure. They will not be tested for labeling purposes.

1. Major surgical events – This will be a composite safety endpoint within 30 days of epicardial surgical procedure, as otherwise defined in the primary safety endpoint.
2. Major catheter events – This will be a composite safety endpoint within 7 days of endocardial catheter procedure, as otherwise defined in the primary safety endpoint.
3. 30-day surgical SAEs - This will include all SAEs that occur within 30 days of the epicardial surgical procedure and that are adjudicated to be related to the device or to the procedure.
4. 12-month DEEP SAEs - This will include all SAEs through the 12-month follow-up visit that are adjudicated to be related to an AtriCure device or to either stage of the DEEP procedure.
5. Unresolved SAEs – This will include all SAEs through the 12-month follow-up visit that are adjudicated to be related to an AtriCure device or to either stage of the DEEP procedure and that are not fully resolved by the 12-month visit. These events shall include any procedure-related deaths, strokes with residual disability, unresolved phrenic nerve damage, or other such events that are adjudicated to have resulted in chronic disability or permanent damage.
6. Any serious adverse event through the 12-month follow-up visit, regardless of attribution.
7. Incidence of stroke or TIA at 12, 24, 36, 48, 60-month visits. The ITT population and the AtriClip effectiveness population will be utilized for analysis of this endpoint.
8. Any esophageal injury that meets all of the following criteria: identified post epicardial ablation, adjudicated by core lab to be a thermal injury with perforation, and related to an AtriCure ablation device, through 30-days post epicardial procedure.

9.6.3 Secondary Endpoints – Health Economics

All health economic endpoints are exploratory in nature.

1. Utilization of cardioversion, defined as the number of cardioversion events (visits) that a subject had in the past 12-month period. This endpoint will be measured at the 12-month, 2-, 3-, 4-, and 5-year (Visits 11-15) follow-up visits.
2. Hospital readmissions for AF, atrial flutter, or atrial tachycardia, defined as the number of readmissions in the past 12-month period. This endpoint will be measured at the 12-month, 2-, 3-, 4-, and 5-year (Visits 11-15) follow-up visits.
3. Total length of stay for all hospital readmissions for AF, atrial flutter, or atrial tachycardia, defined as the sum of the length of stay for each such visit within the last 12-month period.

This endpoint will be measured at the 12-month, 2-, 3-, 4-, and 5-year (Visits 11-15) follow-up visits.

4. Emergency Room Visits for AF, atrial flutter, or atrial tachycardia, defined as the number of visits in the past 12-month period. This endpoint will be measured at the 12-month, 2-, 3-, 4-, and 5-year (Visits 11-15) follow-up visits.

9.7 Analysis of Primary Endpoints

The study will be considered successful if both the primary safety and primary effectiveness endpoints are statistically significant at the 0.025 level (one-sided).

9.7.1 Primary Analyses

Primary Safety

The statistical analysis of the primary safety endpoint will consist of a comparison of the proportion of patients who fail to complete the trial without a primary safety endpoint event to a historical control rate that is based on results from the feasibility trials. Adverse events will be adjudicated in accordance with section 12.1. The proportion of primary safety failures will be calculated with subjects as the experimental unit (i.e., the subject will be considered a failure if a primary safety event was experienced within the timeframes defined in the endpoint). The numerator of the proportion will be the number of subjects who have a primary safety event, and the denominator will be the total number of subjects.

A normal approximation to the binomial distribution, Z-test will be conducted at a one-sided $\alpha=0.025$ level of significance to test the following hypothesis that the proportion of failures is significantly lower than the OPC:

$$H_o : p_s \geq 0.28 \quad vs. \quad H_a : p_s < 0.28$$

where p_s = the proportion of primary safety failures in the safety population. The safety population will be the primary population for this analysis. Missing values will be treated as described in the Missing Values section below.

Primary Effectiveness

The statistical analysis of the primary effectiveness endpoint will consist of a comparison of the proportion of patients who remain a primary effectiveness success at the 12-month visit to a historical control rate that is based on results from the feasibility trials and published literature. The proportion of primary effectiveness successes will be calculated with subjects as the experimental unit (i.e., the subject will be considered a success if no primary effectiveness failure was recorded from the 6-month visit through the 12-month visit). The numerator of the proportion will be the number of subjects who are a primary effectiveness success, and the denominator will be the total number of subjects.

An exact, one-sample binomial test will be conducted at a one-sided $\alpha=0.025$ level of significance to test the following hypothesis that the proportion of effectiveness successes is significantly higher than the OPC:

$$H_o : p_E \leq .60 \quad vs. \quad H_a : p_E > .60$$

where p_E = the proportion of primary effectiveness successes. The ITT population will be the primary population for this analysis and the LOCF method will be the primary missing value method, as described in the Missing Values section below.

9.7.2 Secondary Analyses

All secondary statistical analyses of primary endpoints will be exploratory. All analyses will be conducted using appropriate statistical methods as described in the Statistical Analysis Plan (SAP) for the study. These will include analyses of the populations and subgroups as specified in this protocol and may also include additional populations and/or subgroups.

9.8 Analysis of Secondary Endpoints

An exact, one-sample binomial test will be conducted at a one-sided $\alpha=0.025$ level of significance to test the following hypothesis that the proportion of subjects in the AtriClip effectiveness population with LAA exclusion at the 12-Month Visit (15 months post AtriClip placement) is significantly higher than 80%:

$$H_0 : p_2 \leq .80 \quad vs. \quad H_a : p_2 > .80$$

The last observation carried forward (LOCF) method will be utilized for patients who do not have TEE testing at the 12-Month Visit. This method is considered conservative based on the EXCLUDE study³⁵, which showed a higher exclusion rate at 3 months than at the time of clip placement (98.4% vs. 95.7%).

The remaining secondary endpoints will be exploratory and as such, the data will be tabulated without formal statistical testing.

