When the surgeon is satisfied with the AtriClip position, the surgeon releases the activation lever on the device, allowing the AtriClip to close upon the appendage. At this point, it is important to identify the subject's QRS electrograms to ensure that there are no QRS changes, and no coronary vessels have been occluded. Transesophageal echo (TEE) is examined to ensure that the entire appendage is included within the AtriClip and there is no blood flow to the appendage. A TEE with Doppler will be performed to verify exclusion of the LAA and assess for any residual pouch and also evaluate the base of the LAA along the entire length and depth of the excluded appendage. If not completely excluded, the AtriClip is re-opened and re-deployed. When the AtriClip is satisfactorily positioned around the base of the appendage, the deployment tab is pulled on the applier to fully deploy the AtriClip to the base of the left atrial appendage.

Once deployed, carefully squeeze the activation lever to retract the pull bar against the loop. Providing counter pressure on the AtriClip per the surgeon's discretion, carefully remove the applier deployment loop from the LAA, leaving the AtriClip undisturbed. Gently remove the AtriClip applier device from the thoracic cavity.

After placing the AtriClip LAA Exclusion Device on the Left Atrial Appendage and removing the deployment tool, the surgeon will place the Isolator Pen (MAX5) near the Apex of the LAA. The ASU/ASB dial will be set to PSS on the O.R. lab and the Pen will sense for atrial electrograms. The surgeon will then ask the O.R. lab operator to initiate pacing while the pen is in contact with the Apex of the LAA if the patient is in sinus rhythm. Pacing should be performed at 20 BPM above the intrinsic rate. Electrical isolation of the LAA from the Left Atrium is confirmed if there are no atrial electrograms present during sensing from the LAA or there is no capture during pacing, i.e., the heart rate stays constant and does not equal the pacing rate.

Surgical Stapler Method

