All secondary endpoints for LAA exclusion will utilize the LOCF method for missing values. No missing values will be imputed for the remaining secondary endpoints. If a subject is missing a value for one of these secondary endpoints, they will not be included in the analysis of that endpoint. The number of patients with non-missing values will be reported for each endpoint.

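### LOCF for the LAA exclusion labelling test is called conservative without support; it can inflate the error rate if exclusion is lost after the last early scan, and no sensitivity analysis would show it

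*Protocol*

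**What the plan says.** Protocol 9.6.1 and 9.8 and SAP 5.6.3.1 test the 12-month LAA exclusion rate against 80% in the AtriClip effectiveness population, with an exact binomial test at one-sided 0.025. Protocol 9.6.1 makes the test conditional on primary effectiveness success. The protocol places the endpoint about 15 months after clip placement.

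For missing results, Protocol 9.8 states: "The last observation carried forward (LOCF) method will be utilized for patients who do not have TEE testing at the 12-Month Visit". It then adds: "This method is considered conservative based on the EXCLUDE study". The reason it gives is that exclusion in that study was higher at 3 months than at placement. Section 9.6.1 supplies the counts: "95.7% (67/70) for intra-procedural success and 98.4% (60/61) for 3-month success". SAP 5.3 keeps the method ("All secondary endpoints for LAA exclusion will utilize the LOCF method for missing values"), and SAP 5.6.3.1 repeats it for this endpoint, but the SAP does not repeat the claim that it is conservative.

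The worst-case, best-case and break-even analyses in Protocol 9.9 and SAP 5.3 are written for primary effectiveness. LAA exclusion has LOCF only.

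**The concern.** Conservative is a claim about the direction of bias: carried values should succeed no more often than the unseen 12-month values would. The cited comparison is too small to show a direction and ends at 3 months.

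Two kinds of value can be carried:

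- **Visit 2 intra-operative TEE.** This is the last value for subjects with no evaluable later scan, such as those who leave before the endocardial procedure (Protocol 4.4). It tends to be favourable, because Protocol 5.1.6 says: "If not completely excluded, the AtriClip is re-opened and re-deployed". Protocol 11.3 does not list Visit 2 among the LAA images sent to the core laboratory.
- **Visit 5 TEE.** This is read by the core laboratory about 3 months after placement, with no re-deployment step. It is the last value for subjects lost after the endocardial procedure.

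Neither shows whether exclusion persists for the following year. At stake is a labelling claim that could rest partly on early scans, with nothing planned to reveal it.

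**Working it through.** **1. The plan's own figures.** 67/70 = 95.7% and 60/61 = 98.4%, as stated. The exact two-sided 95% lower limit for 67/70 is 0.8798, which matches the protocol's figure of just under 88%.

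**2. Does 98.4% against 95.7% show a rise?** That is 1 failure in 61 against 3 in 70, a difference of 2.6 points.

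- Treated as independent groups: Fisher two-sided p = 0.62; Newcombe 95% interval for the difference −5.0 to +10.3 points.
- If instead the 61 are a subset of the 70, the comparison is paired. Should the one later failure be an earlier failure, at most 2 subjects improved and none worsened, so the exact sign test gives p ≥ 2 × 0.5² = 0.50. Should it be new, at most 3 improved and 1 worsened, so p ≥ 2 × 5/16 = 0.63. No pairing gives evidence of a rise.
- On the same subset reading, 70 − 61 = 9 subjects have no 3-month result. The 3-month rate among all 70 could lie anywhere from 60/70 = 85.7% to 69/70 = 98.6%.

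**3. What LOCF can do to the test.** From the documents: null rate 0.80, one-sided α = 0.025, exact test. Assumed: n = 200 (the population size is not given; up to 220 are treated), a fraction carried of 5% to 20%, and a success rate q among carried values of 0.75 to 0.957. The 20% borrows the protocol's general attrition allowance, which is not specific to this endpoint.

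Critical count: the smallest r with P(Bin(200, 0.80) ≥ r) ≤ 0.025 is r = 172. Size with nothing missing is 1.8%.

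With m values carried and a true 12-month rate of 0.80, size = P(Bin(200 − m, 0.80) + Bin(m, q) ≥ 172).

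| Rate among carried values, q | 5% carried (m = 10) | 10% (m = 20) | 20% (m = 40) |
|---|---|---|---|
| 0.75 | 1.5% | 1.2% | 0.7% |
| 0.80 (equal to truth) | 1.8% | 1.8% | 1.8% |
| 0.88 (lower limit from step 1) | 2.5% | 3.4% | 6.1% |
| 0.957 (placement rate in the cited study) | 3.3% | 5.9% | 15.9% |

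At n = 220 (critical count 188) and q = 0.957, size is 7.6% with 10% carried and 20.2% with 20%. At n = 150 with 20% carried it is 14.4%. So LOCF is conservative if q is below the true 12-month rate, neutral if equal, and anti-conservative if above.

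**4. Would observed cases alone be safer?** Only if imaging is missing at random. Take n = 200 with a true overall rate of 80%.

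- If the 20 missing subjects have 60% exclusion, the observed rate is (160 − 12)/180 = 0.822, and the observed-case test passes 10.0% of the time.
- If six failed placements drop out of the denominator, the observed rate is 160/194 = 0.825, and it passes 10.8% of the time.

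The second case is plausible. Protocol 7.14 schedules the CTA for subjects in whom a clip was placed, while the analysis population in Protocol 9.5 counts attempts.

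**5. Would missing = failure serve as the test?** At n = 220 it needs 188 exclusions. With 20% missing only 176 can be observed, so it cannot pass. With 10% missing its power at a true rate of 0.957 is 0.77. It is useful as a bound, not as the main analysis.

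**6. The trigger.** Protocol 9.8 and SAP 5.6.3.1 apply LOCF when 12-month TEE is absent. Protocol 7.14 schedules CTA at that visit, with TEE as the fallback. Read literally, subjects with a valid 12-month CTA would have an earlier scan carried over it.

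**The case against.** A reader might infer that carried values are near 100% by design and that the false-positive rate is therefore inflated. The documents do not support that.

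- Protocol 5.1.6 calls for re-deployment but does not promise eventual success. The quoted intra-procedural rate is 95.7%, and the population includes attempts that did not end in a placed clip.
- For subjects lost after the endocardial procedure, the carried value is the Visit 5 scan, to which the re-deployment argument does not apply.
- Inflation needs both missing 12-month imaging and a carried rate above the true 12-month rate. The larger figures suppose a fall from about 96% early to 80% at 15 months, and nothing in the documents reports such a loss.
- If true exclusion stays near 96%, power is about 1.0 under LOCF.
- The test is secondary and follows primary effectiveness success, so its unconditional error cannot exceed the figures above. Subject listings would allow later re-analysis.

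All of this stands, and it limits the point to what can happen. It does not rescue the word conservative, which asserts a direction that the cited data cannot show. Nor does it replace a pre-specified sensitivity analysis for a labelling test.

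**Conclusion.** LOCF is not shown to be conservative for this endpoint. The sole support is a difference indistinguishable from zero, with nine fewer subjects in the later denominator and no data beyond 3 months.

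If exclusion is lost after the last early scan, the nominal 2.5% test can run at 5.9% with 10% carried and 15.9% with 20% carried. This assumes n = 200, a true 12-month rate of 80% and 95.7% success among carried values. With no missing imaging or equal rates there is no inflation. The fraction missing, the population size and the late loss of exclusion are all assumptions.

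The firm findings are the unsupported statement, the lack of any sensitivity analysis for this endpoint, and the TEE trigger that does not match the scheduled CTA. They bear on the labelling claim for LAA exclusion, not on the two primary endpoints.

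**What to change.** 1. Delete from Protocol 9.8 the statement that LOCF is conservative.
2. Keep LOCF as the pre-specified test. Extend to LAA exclusion the worst-case (missing = failure) and break-even analyses already defined for primary effectiveness, the latter reported as a tipping point: how many missing subjects must be successes for the test to pass.
3. Add an observed-case analysis of core-laboratory 12-month imaging that keeps failed placements in the denominator as failures.
4. Report how many values were carried from Visit 2 and how many from Visit 5, and have the labelling conclusion state whether it depends on them.
5. In Protocol 9.8 and SAP 5.6.3.1, change the LOCF trigger to the absence of evaluable 12-month LAA imaging (CTA, or TEE or MRI where used).

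The cost is wording in both documents, a little more analysis and a possibly less favourable supporting estimate. No new data are needed.

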9.9 Missing Endpoints

All safety analysis will utilize the safety population and no missing values will be imputed unless a subject misses a follow-up visit and cannot subsequently be contacted to determine their primary safety status. In this case, the primary safety endpoint will be considered a failure and the subject will be excluded from any subsequent secondary safety analyses for which their status is unknown. If a procedure is aborted due to a primary safety event, the subject will be considered a safety failure. If a subject misses a follow up visit, but it can be subsequently verified that the subject did not incur a safety failure, the subject will be considered a success.

The primary effectiveness analysis will utilize the ITT population and the LOCF method for missing values, as defined below. A subject with any primary effectiveness failure from the 6-month visit through the 12-month visit will be considered a failure for all methods below. Any subjects who withdraw or are lost-to-follow-up prior to the 12-month follow-up visit, or for any reason do not have 12-month ECG readings available, will be analyzed as follows:

- 1) **Last observation carried forward (LOCF):** Any subject who is missing a scheduled testing will be considered an effectiveness success or failure at that scheduled visit based on their status up to and including their last testing.
- 2) **Worst case:** Any subject with no primary effectiveness failure recorded and with no 12-month test data will be considered a failure.
- 3) **Best case:** Any subject with no primary effectiveness failure recorded and with no 12-month test data will be considered a success.
- 4) **Break-even:** If the study endpoint is met using the best-case methodology and is not met using the worst-case methodology, a break-even analysis will be performed to determine the number of subjects with missing endpoint data who would be required to be a success in order

to meet the endpoint.

All secondary endpoints for LAA exclusion will utilize the LOCF method for missing values. No missing values will be imputed for the remaining secondary endpoints. If a subject is missing a value for one of these secondary endpoints, they will not be included in the analysis of that endpoint. The number of patients with non-missing values will be reported for each endpoint.

